7.6.1 Withdrawal Methods

The Sponsor may terminate this study at any time. Reasons for termination may include but are not limited to, the following:

- The incidence or severity of adverse events (AE) in this or other studies point to a potential health hazard for trial subjects.
- Insufficient subject enrollment.
- Any information becoming available during the study that substantially changes the expected benefit risk profile of the study treatments.

7.6.2 Collection of Data from Withdrawn Subjects

In the event that study discontinuation of a randomized subject is necessary, the Investigator should make every attempt to have the subject complete Visit 8 assessments as soon as possible. The reason for premature discontinuation should be recorded in the subject chart and entered in the eCRF.

7.6.3 Subject Replacement

Subjects who withdraw from Cohort 1 will be replaced. Subjects who withdraw from Cohort 2 will not be replaced.

8 SUBJECT TREATMENT

8.1 Treatment Regimen

OTX-CSI contains 0.36 mg of micronized cyclosporine in a resorbable hydrogel matrix. It is intended to be inserted at Visit 2 and retained in the inferior or superior vertical canaliculus where it then provides sustained release of therapeutic levels of cyclosporine over approximately 12 weeks.

8.2 **Prior and Concomitant Therapy**

Only sponsor provided preservative free artificial tears may be used as needed (PRN), if absolutely needed, during the study. Use of AT will be discouraged, and subjects will be counseled to administer only if absolutely necessary. Further, if used, subjects will be instructed not to administer AT with 2 hours prior to any study visit. Preservative-free AT use will be recorded by subjects in a daily diary. All other tears substitutes are not permitted.

Medication	Minimum Washout Period Prior to Screening (Visit 1)
Topical ocular cyclosporine (e.g., Cequa [®] , Restasis [®])	30 days
Lifitegrast (Xiidra®)	30 days
Autolgous tears	30 days
Topical ocular corticosteroids	30 days
Topical ocular antibiotics	30 days
Topical ocular NSAID	30 days
Topical ocular antihistamines and/or mast cell stabilizers	30 days
Topical or nasal vasoconstrictors	30 days
Intranasal Tear Neurostimulation	30 days
Periocular injection of any corticosteroid	90 days
Corticosteroid intra-vitreal depot injection	90 days
Ozurdex	6 months
Retisert	40 months
Isotretinoin	6 months
Systemic Immunosuppressants	6 months

Table 3	List of Prohibited Medications
---------	--------------------------------

8.3 Study Assessments by Visit

For every visit, perform study procedures as referenced in the Schedule of Events (Appendix 1) in the order specified below in both eyes. Note: Procedures will apply to both Cohort 1 and Cohort 2 unless otherwise indicated. An asterisk (*) indicates the assessment may occur at any time during the visit.

8.3.1 Visit 1 (14 days prior to Day 1) Screening/Baseline Visit

Note: In rare cases, the Screening Visit can be split into 2 consecutive days.

- Informed consent
- Demographics *
- Medical/ophthalmic history *
- Record concomitant medications *
- Urine pregnancy test * (may be performed at any time during the visit for WOCBP only)
- VAS for Eye Dryness (Appendix 3)
- OSDI (Appendix 4)
- SPEED assessment (Appendix 5)
- BCVA assessment (Appendix 8)
- Slit lamp biomicroscopy (including punctum assessment) (Appendix 9)
- TBUT (Appendix 11)
- Corneal fluorescein staining (NEI scale) (Appendix 6)

Conjunctival Lissamine Green Staining (NEI scale) (Appendix 7)

• Schirmer Test (without anesthesia) (Appendix 12)

Note: Wait 20 minutes prior to conducting Schirmer

- IOP
- Dilated fundus exam
- Determine Eligibility
- Dispense artificial tears (as needed)
 - **Note**: Subjects will be provided with sponsor supplied Preservative Free Artificial Tear Substitutes but instructed to use only if necessary. If used, instillation will be recorded in a daily diary. Subjects will also be asked to withhold the tears within two hours of study visits.
- Dispense Daily Subject Diary for Artificial Tears Use (as needed) (Appendix 16)

Note: All ophthalmic assessments must be performed on both eyes.

8.3.2 Visit 2 Insertion/Day 1

- Record concomitant medications *
- Record AEs

Note: Any signs, symptoms or conditions captured prior to the insertion of IP, will be recorded as medical history.

- Collect and review Subject Daily Diary for Artificial Tears Use (as needed)
 Note: Subjects using AT > 3x/day for 3 consecutive days will be ineligible for randomization.
- VAS for Eye Dryness
- OSDI
- SPEED assessment
- BCVA assessment
- Slit lamp biomicroscopy, including punctum assessment **Note:** Prior to insertion, a clinical determination of the absence of infection will be made based on the lack of erythema or discharge at the punctum.
- Punctum Size Assessment
- TBUT
- Corneal fluorescein staining (NEI scale)
- Conjunctival Lissamine Green Staining (NEI scale) Schirmer Test (without anesthesia)

Note: Wait 20 minutes prior to conducting Schirmer

- IOP
- Determine Eligibility for Insertion (Cohort 1 and 2) and Randomization (Cohort 2)
- OTX-CSI or HV Insert Placement (Appendix 13)
 Note: If placement is only successful in one eye, subjects should be asked to return within 0-3 days to re-attempt insertion in the other eye.
- Ease of Insertion Assessment
- Systemic PK (at selected sites to be collected 2 hours (±30 minutes) or 4 hours (±30 minutes) post-insertion) (Appendix 10)
- Tear film PK (to be collected 1 hour (±30 minutes), 2 hours (±30 minutes) and 4 hours (±30 minutes) post-insertion)
- Dispense artificial tears (as needed)
- Dispense Daily Subject Diary for Artificial Tear Use (as needed)

Note: All ophthalmic assessments must be performed on both eyes.
8.3.3 Visit 2B (Day 1 + 1 to 3 days)

This visit should be conducted for subjects with a successful unilateral insertion at Visit 2 (Day 1) to reattempt insertion in the other eye. The following assessments should be performed at this visit:

- OTX-CSI or HV Insert Placement (Appendix 13)
- Ease of Insertion Assessment
- Systemic PK (at selected sites to be collected 2 hours (±30 minutes) or 4 hours (±30 minutes) post-insertion) (Appendix 10)
- Tear film PK (to be collected 1 hour (±30 minutes), 2 hours (±30 minutes) and 4 hours (±30 minutes) post-insertion)

8.3.4 Follow-Up Visit 3 (Week 2 ±2 days)

- Record concomitant medications *
- Record AEs *
- Collect and review Subject Daily Diary for Artificial Tear Use (as needed) *
- VAS for Eye Dryness
- OSDI
- SPEED assessment
- BCVA assessment
- Slit lamp biomicroscopy, including punctum assessment
- OTX-CSI or HV Insert Presence by visual Assessment
- Ease of Visualization by Investigator (Appendix 14)
- Corneal fluorescein staining (NEI scale)
- Conjunctival Lissamine Green Staining (NEI scale)
- Systemic PK (at selected sites)

Note: Wait 20 minutes prior to conducting Schirmer/Tear Film PK

- Schirmer Test (without anesthesia) and Tear Film PK
- Dispense artificial tears (as needed)
- Dispense Daily Subject Diary for Artificial Tear Use (as needed)

Note: All ophthalmic assessments must be performed on both eyes.

8.3.5 Follow-Up Visit 4 (Week 4 ±2 days)

- Record concomitant medications *
- Record AEs*
- Collect and review Subject Daily Diary for Artificial Tear Use (as needed) *
- VAS for Eye Dryness
- OSDI
- SPEED assessment
- BCVA assessment
- Slit lamp biomicroscopy, including punctum assessment
- OTX-CSI or HV Insert Presence by visual Assessment
- Ease of Visualization by Investigator
- Corneal fluorescein staining (NEI scale)
- Conjunctival Lissamine Green Staining (NEI scale) Schirmer Test (without anesthesia) and Tear Film PK

Note: Wait 20 minutes prior to conducting Schirmer/Tear Film PK

- Dispense artificial tears (as needed)
- Dispense Daily Subject Diary for Artificial Tear Use (as needed)

Note: All ophthalmic assessments must be performed on both eyes.

8.3.6 Follow-Up Visit 5 (Week 6 ±3 days)

- Record concomitant medications *
- Record AEs *
- Collect and review Subject Daily Diary for Artificial Tear Use (as needed) *
- VAS for Eye Dryness
- OSDI
- SPEED assessment
- BCVA assessment
- Slit lamp biomicroscopy, including punctum assessment
- OTX-CSI or HV Insert Presence by visual Assessment
- Ease of Visualization by Investigator
- TBUT
- Corneal fluorescein staining (NEI scale)

Conjunctival Lissamine Green Staining (NEI scale)Schirmer Test (without anesthesia)/Tear Film PK

Note: Wait 20 minutes prior to conducting Schirmer/Tear Film PK

- Dispense artificial tears (as needed)
- Dispense Daily Subject Diary for Artificial Tear Use (as needed)

Note: All ophthalmic assessments must be performed on both eyes.

8.3.7 Follow-Up Visit 6 (Week 9 ±3 days)

- Record concomitant medications *
- Record AEs *
- Collect and review Subject Daily Diary for Artificial Tear Use (as needed) *
- VAS for Eye Dryness
- OSDI
- SPEED assessment
- BCVA assessment
- Slit lamp biomicroscopy, including punctum assessment
- OTX-CSI or HV Insert Presence by visual Assessment
- Ease of Visualization by Investigator
- Corneal fluorescein staining (NEI scale)
- Conjunctival Lissamine Green Staining (NEI scale)
- Schirmer Test (without anesthesia) and Tear Film PK

Note: Wait 20 minutes prior to conducting Schirmer/Tear Film PK

- Dispense artificial tears (as needed)
- Dispense Daily Subject Diary for Artificial Tear Use (as needed)

Note: All ophthalmic assessments must be performed on both eyes.

8.3.8 Follow-Up Visit 7 (Week 12 ±3 days)

- Record concomitant medications *
- Record AEs *
- Collect and review Subject Daily Diary for Artificial Tear Use (as needed) *
- VAS for Eye Dryness
- OSDI
- SPEED assessment
- BCVA assessment
- Slit lamp biomicroscopy, including punctum assessment
- OTX-CSI or HV Insert Presence by visual Assessment
- Ease of Visualization by Investigator
- TBUT
- Corneal fluorescein staining (NEI scale)
- Conjunctival Lissamine Green Staining (NEI scale)
- Schirmer Test (without anesthesia) and Tear Film PK Note: Wait 20 minutes prior to conducting Schirmer/Tear Film PK
- Dispense artificial tears (as needed)
- Dispense Daily Subject Diary for Artificial Tear Use (as needed)

Note: All ophthalmic assessments must be performed on both eyes.

8.3.9 Final Visit 8 (Week 16 ±3 days)

- Record concomitant medications *
- Record AEs *
- Collect and review Subject Daily Diary for Artificial Tear Use (as needed) *
- Urine pregnancy test (WOCBP only)
- VAS for Eye Dryness
- OSDI
- SPEED assessment
- BCVA assessment
- Slit lamp biomicroscopy, including punctum assessment
- OTX-CSI or HV Insert Presence by visual Assessment
- Ease of Visualization by Investigator
- Corneal fluorescein staining (NEI scale)
- Conjunctival Lissamine Green Staining (NEI scale)
- Schirmer Test (without anesthesia) and Tear Film PK

Note: Wait 20 minutes prior to conducting Schirmer/Tear Film PK

- Undilated Fundus Exam (*may be performed before or after IOP)
- IOP
- Punctum Size Assessment
- Dispense artificial tears (as needed)
- Dispense Daily Subject Diary for Artificial Tear Use (as needed)

Note: All ophthalmic assessments must be performed on both eyes.

8.3.10 30-day Follow-Up Visit (Week 20 ± 10 days)

This visit will be conducted every 30 days (\pm 10 days) until an insert can no longer be visualized and the physician has determined that there is no evidence of biological activity.

- Record concomitant medications *
- Record AEs *
- Collect and review Subject Daily Diary for Artificial Tear Use (as needed) *
- VAS for Eye Dryness
- OSDI
- SPEED assessment
- BCVA assessment
- Slit lamp biomicroscopy, including punctum assessment
- OTX-CSI or HV Insert Presence by visual Assessment
- Ease of Visualization by Investigator
- Corneal fluorescein staining (NEI scale)
- Conjunctival Lissamine Green Staining (NEI scale) Schirmer Test (without anesthesia) and Tear Film PK Note: Wait 20 minutes prior to conducting Schirmer/Tear Film PK
- Dispense artificial tears (as needed)
- Dispense Daily Subject Diary for Artificial Tear Use (as needed)

Note: All ophthalmic assessments must be performed on both eyes.

8.3.11 Replacement of Inserts

For Cohort 1 subjects only, within the first six weeks post treatment, if an insert is not visualized in one or both eyes by the Investigator, the Investigator should place a new insert in the respective eye(s) after confirming patency. Refer to Appendix 13 for placement instructions. Replacement of inserts is not permitted for subjects enrolled in Cohort 2.

8.3.12 Unscheduled Visit

An unscheduled visit may be performed during the course of the trial in order to ensure subject safety. All procedures performed at an unscheduled visit will be recorded in the source documents and on the Unscheduled Visit eCRF pages.

Evaluations that may be conducted at an Unscheduled Visit may include:

- Slit lamp biomicroscopy
- BCVA assessment
- IOP
- Dilated or Undilated fundus exam
- Urine pregnancy test (if applicable)
- Assessment of AEs
- Assessment of concomitant medications and/or treatments
- Any other assessments needed in the judgment of the investigator

9 ASSESSMENT OF EFFICACY

9.1 Efficacy Parameters

The efficacy assessments of the study are listed below and will be performed per the Schedule of Events in Appendix 1. All clinical efficacy assessments should be performed in both eyes. Efficacy assessments should be performed by the same person, e.g., FCS scoring for a given subject should be performed by the same person at each visit if possible.

The following efficacy measures will be assessed:

Signs

- Percent of subjects with ≥ 10 mm increase in Schirmer at Week 12.
- Schirmer Test (without anesthesia) change from baseline (CFB) and absolute value at Week 12.
- Total Corneal Fluorescein Staining (tCFS) using NEI scale, CFB and absolute values at each post baseline study visit.
- CFS sub-regions using NEI scale, CFB and absolute values at each post-baseline visit.
- Conjunctival Lissamine Green Staining using NEI Scale, CFB and absolute values at each postbaseline visit.

Symptoms (subject-reported)

- Eye Dryness Score (visual analogue scale [VAS]), CFB and absolute values at each post-baseline visit.
- Ocular Surface Disease Index questionnaire (OSDI[©]) questionnaire, CFB and absolute values at each post-baseline visit (total score and each of the three domains).
- SPEED questionnaire, CFB at each post-baseline visit.

Other Efficacy Evaluations

- Tear Film Break Up Time (TBUT), CFB at Week 12.
- Presence of OTX-CSI or HV insert at all post-baseline visits.
- Ease of insertion as assessed by the Investigator.
- Ease of visualization as assessed by the Investigator.

10 ADVERSE EVENTS

The investigator and study staff are responsible for detecting and recording AEs and SAEs, during scheduled safety evaluations and whenever such information is brought to their attention.

This section of the protocol provides definitions and detailed procedures to be followed.

During each visit, the Investigator will question the subject about adverse events using an open question taking care not to influence the subject's answers. Throughout the course of the study, every effort must be made to remain alert to possible AEs. If an AE occurs, the first concern should be for the safety of the subject. If necessary, appropriate medical intervention should be provided. At the signing of the ICF, each subject must be given the names and telephone numbers of study site staff for reporting AEs and medical emergencies.

10.1 Definition of an Adverse Event

An AE is any untoward medical occurrence in a patient or clinical investigation subject administered a pharmaceutical product and that does not necessarily have a causal relationship with this treatment. An AE can therefore be any unfavorable and unintended sign (including an abnormal laboratory finding), symptom, or disease temporally associated with the use of a medicinal (investigational) product, whether or not related to the medicinal (investigational) product. Examples of an AE include:

- Exacerbation of a pre-existing condition including either an increase in frequency and/or intensity of the condition.
- New conditions detected or diagnosed after IP administration even though it may have been present prior to the start of the study.
- Signs, symptoms of a drug interaction.

- Signs, symptoms of a suspected overdose of either IP or a concurrent medication (overdose per se should not be reported as an AE/SAE).
- A laboratory abnormality occurring after the start of the study (i.e., after insertion) that results in subject withdrawal from the study or medical treatment or further follow-up.

10.2 Definition of Serious Adverse Event

An SAE is any untoward medical occurrence that at any dose:

- Results in death.
- Is life-threatening.
 - **Note:** The term "life-threatening" refers to an event in which the subject was at risk of death at the time of the event; it does not refer to an event which hypothetically might have caused death if it were more severe.
- Requires in-patient hospitalization or prolongation of existing hospitalization. Hospitalizations for elective surgeries do not constitute an SAE.
- Results in persistent or significant disability/incapacity.
- Is a congenital abnormality/birth defect.

Medical and scientific judgment should be exercised in deciding whether other situations should be considered SAEs, such as important medical events that might not be immediately life threatening or result in death or hospitalization but might jeopardize the subject or might require intervention to prevent one of the other outcomes listed above.

10.3 Disease-Related Events or Outcomes Not Qualifying as AE/SAE's

Not applicable.

10.4 Monitoring and Recording of AEs and SAEs

10.4.1 Adverse Events

Any AE experienced by the subject from Visit 2 (Insertion/Day 1) through Visit 9 (30-day follow-up visit) is to be recorded in the eCRF, regardless of the severity of the event or its relationship to study treatment.

Any AEs already documented at a previous assessment and designated as ongoing, should be reviewed at subsequent visits, as necessary. If these have resolved, this should be documented.

Changes in intensity or frequency of AEs should be recorded as separate events (i.e., a new record started).

10.4.2 Serious Adverse Events

Any SAE experienced by the subject from Visit 2 (Insertion/Day 1) through Visit 9 (30-day follow-up visit) is to be recorded on an SAE Form, regardless of the severity of the event or its relationship to study treatment.

Any SAE ongoing when the subject completes the study or discontinues from the study will be followed by the Investigator until the event has resolved, stabilized, or returned to baseline status.

10.4.3 All Events

All events must be assessed to determine the following:

• If the event meets the criteria for an SAE as defined in Section 10.2.

- The severity of the event as defined in Section 10.7.1.
- The relationship of the event to study treatment as defined in Section 10.7.2.

10.5 Immediate Reporting of Serious Adverse Events and Pregnancies

In order to adhere to all applicable laws and regulations for reporting an SAE or pregnancy, the study site must formally notify the pharmacovigilance team within 24 hours of the study site staff becoming aware of the SAE or pregnancy. It is the Investigator's responsibility to ensure that the SAE or pregnancy reporting information is emailed or faxed as described in Figure 2. It may be necessary for the pharmacovigilance team to directly communicate with the Investigator if additional information is required.

After the initial SAE report, the investigator is required to proactively follow each subject and provide further information to the pharmacovigilance team on the subject's condition within 24 hours. New or updated information will be recorded on the SAE reporting form. The updated SAE reporting form should be sent to the pharmacovigilance team within 24 hours as described in Figure 2.

All additional follow-up evaluations must be reported to the pharmacovigilance team. Such data should be sent by fax or email (Figure 2) within 10 calendar days. All SAEs will be followed until the Investigator and Ocular Therapeutix agree that the event is satisfactorily resolved.

10.6 Death

The death must be recorded on the appropriate eCRF. All causes of death must be reported as SAEs. The Investigator should make every effort to obtain and send death certificates and autopsy reports to the pharmacovigilance team.

Figure 2 Reporting Information for SAEs and Pregnancies

To report initial or follow up SAE or Pregnancy information email or fax a copy of the SAE or Pregnancy report form to the following:

ProPharma Group

Email: [contact]

[contact]

10.7 Evaluating AEs and SAEs

10.7.1 Severity

The following definitions should be considered when evaluating the severity of AEs and SAEs.

- **Mild** Event is noticeable to the subject, but is easily tolerated and does not interfere with the subject's daily activities.
- **Moderate** Event is bothersome, possibly requiring additional therapy, and may interfere with the subject's daily activities.
- **Severe** Event is intolerable, necessitates additional therapy or alteration of therapy, and interferes with the subject's daily activities.

For AEs that change in intensity, the start and stop date of each intensity should be recorded.

An AE that is assessed as severe should not be confused with a SAE. An event is defined as 'serious' when it meets one of the pre-defined outcomes as described in Section 10.2 Definition of a SAE.

10.7.2 Relationship to OTX-CSI or Hydrogel Vehicle product or procedure

The following definitions should be considered when evaluating the relationship of AEs and SAEs to the study treatment:

Unrelated	This category applies to those (S)AEs which, after careful consideration, are clearly and incontrovertibly due to extraneous causes (disease, environment, etc.); there is no reasonable probability that the (S)AE may have been caused by the insertion procedure or the ophthalmic insert. If the investigator determines that the AE is unlikely to be related to the study drug, then this would be the appropriate category.
Related	The following criteria should be applied in considering inclusion of an (S)AE in this category:
	i. It bears a reasonable temporal relationship to the insertion procedure or the presence of the ophthalmic insert
	 ii. It could not be reasonably explained by the known characteristics of the subject's clinical state, environmental or toxic factors or other factors (e.g., disease under study, concurrent disease(s) and concomitant medications) and modes of therapy administered to the subject
	iii. It disappears or decreases on removal of the ophthalmic insert
	iv. It follows a known pattern of response to the insertion procedure or the ophthalmic insert

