4 BACKGROUND INFORMATION

4.1 Dry Eye Disease (DED)

Dry eye disease (DED), also known as Keratoconjunctivitis Sicca (KCS), is one of the most common ophthalmic disorders presenting to the clinician (American Academy of Ophthalmology, 2018). It is estimated that more than 16 million United States (US) adults have been diagnosed with the disorder with 9 million being classified as moderate to severe (Farrand et al, 2017; Prevent Blindness, 2019). Prevalence of dry eye is higher among women than men (8.8% or approximately 11.1 million compared to 4.5% or 5.3 million, respectively) (Farrand et al, 2017). Prevalence also increases with age with 2.7% of Americans age 18 to 34 years and 18.6% of Americans \geq 75 years diagnosed with DED (Farrand et al, 2017).

DED is a multifactorial disorder of the tear film and ocular surface that results in eye discomfort (such as burning sensation, itching, redness, stinging, pain, and foreign body sensation), visual disturbances, tear film instability, and often ocular surface damage (Perry, 2008; Schultz, 2014). Inflammation of both the lacrimal gland and ocular surface has been shown to play a role in dry eye, resulting in a reduction in tear production (Salib et al, 2006; Sall et al, 2000; Stevenson et al, 2000; Willen et al, 2008). In animal models, T-cell-mediated inflammation was both a cause and result of dry eye (Niederkorn et al, 2006). In humans, dry eye was found to be associated with the presence of conjunctival T-cells and elevated levels of inflammatory cytokines in the tears compared with controls (Massingale et al, 2009; Lee et al, 2013).

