Appendix 2 Safety Review Group Charter

The recommendation to continue into Cohort 2 (double-masked, vehicle-controlled, portion of the study) will be the responsibility of a Safety Review Group constituted by the Principal Investigator(s) of the study, the Medical Monitor and the Chief Medical Officer at Ocular Therapeutix, Inc. The SRG, may request the participation of an independent statistician and/or independent medical expert to assist in the assessment of the safety of the IP and the recommendation to progress.

In order to maintain the integrity of the trial, unless it is absolutely necessary, the safety review should be conducted using masked subjectspecific information. The Safety Review Group will convene after all subjects in Cohort 1 have been followed for at least 2 weeks (or at any time during the study if necessary) to evaluate the safety of the IP. Upon review and evaluation, the SRG will issue a recommendation to Ocular Therapeutix, Inc.

General guidelines for the recommendation to escalate to the next cohort:

A recommendation to escalate to the next cohort may be issued if no more than 1 dose limiting toxicity (DLT) is found during or at the end of the cohort.

Indicators of DLT in this study will be assessed according to the Common Terminology Criteria for Adverse Events (CTCAE) (version 5.0, Published November 27, 2017).

A DLT is defined as one of the following events at the specified toxicity level deemed by the Investigator to be related to OTX-CSI and based on CTCAE (version 5.0)¹

- Any Grade 3 or higher adverse event
- Any Grade 2 or higher adverse event that in the judgment of the Investigator or Sponsor requires discontinuation of dosing
- Any Grade 2 or higher adverse event that in the judgment of the Investigator or Sponsor requires further investigation before determining dose escalation.

Events, including serious adverse events (SAEs), deemed by the Investigator to be related to the subject's underlying medical condition, will not be considered DLTs and used for determination of dose escalation, e.g., hyperglycemic event.

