Document Version No.:	V1.0	Document Date:	01-OCT-2021

- Table 14.2.3.15.4 The Summary of Individual Questions of Second and Third Sections of Standard Patient Evaluation of Eye Dryness (SPEED) (Frequency and Severity of Symptoms) by Visit PP
- Table 14.2.3.16.1: The Summary and Linear Model of Change from Baseline inStandard Patient Evaluation of Eye Dryness (SPEED) total score and its individual questions at each Post-Baseline Visits mITT
- Table 14.2.3.16.2: The Summary and Linear Model of Change from Baseline inStandard Patient Evaluation of Eye Dryness (SPEED) total score and its individual questions at each Post-Baseline Visits PP
- Table 14.2.4.1.1: The Summary and Linear Model of Change from Baseline in TFBUT average on Study Eye at Visit 7 (Week 12) mITT
- Table 14.2.4.1.2: The Summary and Linear Model of Change from Baseline in TFBUT average on Non-Study Eye at Visit 7 (Week 12) mITT
- Table 14.2.4.2.1: Ease of Insertion as Assessed by the Investigator on Study Eye at Visit 2 (or Visit 2B) mITT
- Table 14.2.4.2.2: Ease of Insertion as Assessed by the Investigator on Non-Study Eye at Visit 2 (or Visit 2B) mITT
- Table 14.2.4.3.1: The Presence of Insert on Study Eye at each Post-Baseline Visits mITT
- Table 14.2.4.3.2: The Presence of Insert on Non-Study Eye at each Post Baseline-Visits mITT
- Table 14.2.4.4.1: Ease of Visualization as Assessed by Investigator on Study Eye at each Post-Baseline Visits mITT
- Table 14.2.4.4.2: Ease of Visualization as Assessed by Investigator on Non-Study Eye at each Post-Baseline Visits mITT
- Table 14.3.1: Overview of Treatment-Emergent Adverse Events (TEAEs) SAFETY
- Table 14.3.2.1: Ocular Treatment-Emergent Adverse Events (TEAEs) by System Organ Class and Preferred Term SAFETY
- Table 14.3.2.2: Non-Ocular Treatment-Emergent Adverse Events (TEAEs) by System Organ Class and Preferred Term SAFETY
- Table 14.3.2.3: Ocular Treatment-Emergent Adverse Events (TEAEs) by Preferred Term
- Table 14.3.2.4: Non-Ocular Treatment-Emergent Adverse Events (TEAEs) by Preferred Term
- Table 14.3.3.1: Ocular Serious Treatment-Emergent Adverse Events (TEAEs) by System Organ Class and Preferred Term SAFETY
- Table 14.3.3.2: Non-Ocular Serious Treatment-Emergent Adverse Events (TEAEs) by System Organ Class and Preferred Term – SAFETY
- Table 14.3.4.1: Ocular Treatment-Emergent Adverse Events (TEAEs) Related to IP by System Organ Class and Preferred Term SAFETY

Sponsor:	Ocular Therapeutix, Inc.		
Protocol:	CLN-Protocol-0054		

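### The Unrelated definition in Protocol 10.7.2 contradicts itself, and one procedure-or-product code is reported in the SAP as related to IP, so a procedural injury can be coded or labelled wrongly

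*Protocol*

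**What the plan says.** Protocol 10.4.3 makes 10.7.2 the causality definition for all events. Section 10.7.2 has two categories.

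- **Unrelated** opens by requiring that the event be "clearly and incontrovertibly due to extraneous causes (disease, environment, etc" and that "there is no reasonable probability that the (S)AE may have been caused by the insertion procedure or the ophthalmic insert". It closes with "If the investigator determines that the AE is unlikely to be related to the study drug, then this would be the appropriate category".
- **Related** is introduced by "The following criteria should be applied in considering inclusion of an (S)AE in this category". Four criteria follow: (i) reasonable timing relative to the procedure or the insert; (ii) no reasonable explanation by other factors ("e.g., disease under study, concurrent disease(s) and concomitant medications"); (iii) improvement when the insert is removed; (iv) a known response pattern to the procedure or the insert.

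Protocol 4.4 lists the risks of the insertion procedure separately from those of topical cyclosporine. Trauma to the punctum is on the procedure list.

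SAP 4.9 reports relationship to treatment at two levels, unrelated and related. SAP 7.1 titles Table 14.3.4.1 "Ocular Treatment-Emergent Adverse Events (TEAEs) Related to IP by System Organ Class and Preferred Term SAFETY". Tables 14.3.4.2 to 14.3.4.4 use the same label for non-ocular and serious events. No table of procedure-related events is listed.

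Protocol Appendix 2 counts as a dose-limiting toxicity (DLT) an event "deemed by the Investigator to be related to OTX-CSI and based on CTCAE" grading. It names neither the procedure nor 10.7.2.

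**The concern.** A causality definition should lead two careful investigators to the same code for the same event. Here one sentence of Unrelated can exclude an event that the next sentence admits, and the Related criteria do not settle the matter.

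The code also answers a different question from the one its tables ask. Investigators judge procedure or product together, while the table titles speak of the product alone. For an insert placed after punctal dilation, injury from placement and a reaction to the insert or the drug are different safety messages. A reader of the related-event tables could not tell them apart, and could not know whether procedural injuries were included.

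Two further uses depend on a causality judgement. Under SAP 4.9, one route by which an event present at baseline becomes treatment-emergent is being considered drug-related. Under Protocol 10.9.3, SUSAR status requires that the event be judged associated with study treatment.

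**Working it through.** The plan states no figure on this point, so the check sets the passages side by side.

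**Step 1: the two sentences of Unrelated.**

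| | Opening sentence | Closing sentence |
|---|---|---|
| Threshold | extraneous cause beyond dispute, no reasonable probability otherwise | merely unlikely |
| Scope | insertion procedure or insert | study drug |

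Both rows differ, so there are two rules under one heading.

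**Step 2: three test events.**

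| Event | Unrelated, opening sentence | Unrelated, closing sentence (literal) | Related criteria |
|---|---|---|---|
| A. Punctal trauma from dilation | barred: the procedure caused it | admitted: unlikely to be due to the drug | i and iv met; iii is no test of a dilator injury |
| B. Event with a small but real chance of being caused by the insert | barred: not beyond dispute | admitted: unlikely | depends on the event |
| C. Foreign body sensation, insert still in place | not met: not beyond dispute | depends on the investigator's judgement | i can be met; ii doubtful, since dry eye can explain it; iii cannot be judged; iv can be met, since Protocol 4.4 lists it for the procedure |

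A and B show the contradiction within Unrelated. C shows the open combination rule: if all four criteria are needed, the event is not Related; if any one is enough, it is. The text does not choose.

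**Step 3: event A in the SAP output.** Coded Related, it enters Table 14.3.4.1 as an IP-related event. Coded Unrelated, it is absent from all four related tables. Neither result reports it as what it is, an event due to the procedure.

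**Step 4: how many outputs are touched.** The adverse event tables in SAP 7.1 are 14.3.1 (1), 14.3.2.1 to 14.3.2.4 (4), 14.3.3.1 to 14.3.3.2 (2), 14.3.4.1 to 14.3.4.4 (4) and 14.3.5.1 to 14.3.5.2 (2): 1 + 4 + 2 + 4 + 2 = 13. Four of the 13 are defined by relatedness. The by-relationship counts called for in SAP 4.9 are also affected, wherever they are displayed. The other tables use causality only through the clause on events present at baseline.

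**The case against.** **Study drug may be loose wording.** The documents use the term for the administered product elsewhere, for instance in Protocol 6.6 and 7.6. The closing sentence also follows one that sets the scope as procedure or insert. Read in context, it may only give an unlikely relationship a home on a two-level scale. This softens the scope conflict, but the threshold conflict remains, and investigators should not have to infer the scope of a causality rule.

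**Merging procedure and product is defensible.** The insert cannot be given without the procedure, and the text of SAP 4.9 speaks of treatment, which fits 10.7.2. That stands as a design choice. It does not support the IP label on the tables.

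**The eCRF may already split the attribution.** It is not among the documents, so this is possible. Neither the protocol nor the SAP says so, and the SAP lists no output that would use the split.

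**A reader might infer that drug irritation resembling dry eye must be coded Unrelated, or fits neither category.** Of the nine topical-cyclosporine reactions in Protocol 4.4, seven match features that Protocol 4.1 gives for dry eye: six among "burning sensation, itching, redness, stinging, pain, and foreign body sensation", plus visual disturbance. Criterion ii does weigh against such events. But the text never says that criteria ii and iii must both be met, and criteria i and iv can point to Related. The defect is the unstated rule, not a bar.

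**A reader might infer that the DLT count rests on this code.** Appendix 2 has its own attribution wording and its own exclusion of events due to the underlying condition. It does not cite 10.7.2, and the progression review concerns about 5 open-label subjects. What stands is that the two passages are not reconciled.

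**Conclusion.** The point holds as a definitional fault with limited reach. Unrelated carries two thresholds and two scopes, Related has no combination rule, and a merged code is reported under a product label. A procedural injury can therefore be left out of the related tables or be shown in them as IP-related, with the text followed either way.

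The reach is the four related-event tables, the by-relationship counts, the drug-related clause for events present at baseline, and the association judgement for SUSARs. It would be wrong to conclude that the OTX-CSI versus vehicle safety comparison fails. The primary safety evaluation is adverse events as such (Protocol 6.2.1), and they are recorded whatever their relationship (10.4.1). Cohort 2 is masked and all its arms undergo insertion, so all-event comparisons largely stand.

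No number of affected subjects can be given, because the documents state no rate of procedural events and any count would only restate an assumed rate. The conclusion rests on reading 10.7.2 as written and on the absence of any separate procedure attribution in the protocol or SAP.

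**What to change.** 1. In Protocol 10.7.2, give Unrelated one threshold and one scope. Delete the closing sentence, or restate it so that it covers both the procedure and the insert.
2. State that criteria i to iv are considerations that need not all be met, and that this applies also when the insert has not been removed.
3. Record attribution to the insertion or removal procedure, and attribution to the insert or drug, as two judgements, if the eCRF does not already do so.
4. In the SAP, base Tables 14.3.4.1 to 14.3.4.4 on the insert-or-drug attribution, and tabulate procedure-related events separately.
5. The sponsor should reconcile the attribution wording in Appendix 2 with 10.7.2. No DLT rule is proposed here.

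The cost is protocol and SAP wording, at most one extra field, and one table split. Somewhat more events may be classed as related.
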